### 517 **13. RANDOMISATION PROCEDURE AND BREAKING OF BLINDED CODES**

518

519 The trial is a double-blind trial. A randomization session will be carried out for all patients by using the  
520 blinded randomization list. At the randomization visit patients meeting all inclusion/exclusion criteria will  
521 be randomized to one of two parallel treatments groups:

522 **Group A:** (i) 7-week subcutaneous liraglutide treatment once daily, (ii) a 4-week wash-out period,  
523 and (iii) 7-week subcutaneous placebo once daily.

524 **Group B:** (i) 7-week subcutaneous placebo once daily, (ii) a 4-week wash-out period, and (iii) 7-  
525 week subcutaneous liraglutide treatment once daily.

526

527 **13.1 Breaking of blinded codes:** If the site needs to break the treatment code, the sponsor should, if  
528 possible, be contacted before the code is broken.

529

530 The code for a particular patient may be broken in a medical emergency if knowing the actual treatment  
531 would influence the treatment of the patient. The reason for code break should be documented in the  
532 medical record. Whenever a code is broken the person breaking the code must print the Code Break  
533 Confirmation Notification, and sign and date the document.

534

535 If the code has been broken, the patient should be discontinued from the trial product but be asked to  
536 continue in the trial.

537

538

## 539 **14. ASSESSMENT OF SAFETY**

540

### 541 **14.1. Definitions**

542 **An Adverse Event (AE) is** any untoward medical occurrence in a patient or clinical investigation  
543 participants administered a medicinal product, which does not necessarily have to have a causal  
544 relationship with this treatment (the study medication).

545 **An Adverse Reaction (AR) is** all untoward and unintended responses to a medicinal product related  
546 to any dose. The phrase "responses to a medicinal product" means that a causal relationship between  
547 a study medication and an AE is at least a reasonable possibility, i.e., the relationship cannot be ruled  
548 out.

549 **A Serious Adverse Event (SAE) is an experience that at any dose results in any of the following:** (1)  
550 **Death;** (2) **Life-threatening experience;** (3) **Inpatient hospitalization or prolongation of existing**  
551 **hospitalization;** (4) **A persistent or significant disability/incapacity;** or (5) **A congenital anomaly/birth**  
552 **defect. Important medical events that may not result in death, be life-threatening, or require**  
553 **hospitalization may be considered an SAE when, based upon appropriate medical judgement, they**  
554 **may jeopardise the patient or require medical or surgical intervention to prevent one of the outcomes**  
555 **listed in this definition. Suspicion of transmission of infectious agents must be always be considered**  
556 **an SAE. Note: the term "life-threatening" in the previous definition of SAE refers to an event in which**  
557 **the patient was at risk of death at the time of the event; it does not refer to an event which**  
558 **hypothetically might have caused death if it was more severe.**

559 **A Serious Adverse Reaction (SAR) is** an adverse event (expected or unexpected) that is both  
560 serious and, in the opinion of the reporting investigator, believed with reasonable probability to be due  
561 to one of the study treatments, based on the information provided.

562 **A Suspected Unexpected Serious Adverse Reaction (SUSAR) is:**

563 A serious adverse reaction, the nature or severity of which is not consistent with the applicable product  
564 information (e.g. Investigator's Brochure for an unapproved investigational product or summary of  
565 product characteristics for an approved product).

566

567 **14.2 Causality:** The relationship of each adverse event to the trial medication must be determined by a  
568 medically qualified individual according to the following definitions:

569 **Related:** The adverse event follows a reasonable temporal sequence from trial medication administration.  
570 It cannot reasonably be attributed to any other cause.

571 **Not Related:** The adverse event is probably produced by the participant's clinical state or by other modes  
572 of therapy administered to the participant.

573

574 **14.3. Procedures for recording adverse events:** All AEs occurring during the study observed by the  
575 investigator or reported by the participant, whether or not attributed to study medication, will be recorded  
576 on the CRF. The following information will be recorded: study name, patient identification (e.g., patient  
577 number, sex, and age), trial drug, description of the event and diagnosis when possible, date of onset and  
578 end date, severity, assessment of relatedness to study medication, other suspect drug or device, action  
579 taken, and reporter. Follow-up information should be provided as necessary. AEs considered related to  
580 the study medication as judged by a medically qualified investigator or the sponsor will be followed until  
581 resolution or the event is considered stable. All related AEs that result in a participant's withdrawal from  
582 the study or are present at the end of the study, should be followed up until a satisfactory resolution  
583 occurs.

584

585 It will be left to the investigator's clinical judgment whether or not an AE is of sufficient severity to require  
586 the participant's removal from treatment. If either of these occurs, the participant must undergo an end of  
587 study assessment and be given appropriate care under medical supervision until symptoms cease or the  
588 condition becomes stable. The relationship of AEs to the study medication will be assessed by a  
589 medically qualified investigator. Any pregnancy occurring during the clinical study and the outcome of the  
590 pregnancy, should be recorded and followed up for congenital abnormality or birth defect.

591

592 **14.4. Reporting procedures for serious adverse events:** All SAEs must be reported to the Sponsor or  
593 designated organization within one working day of discovery or notification of the event. The Sponsor or  
594 designated organization will perform an initial check of the report, request any additional information. All  
595 SAE information must be recorded on an SAE forms and faxed to the Sponsor or designated  
596 organization. Additional information received for a case (follow-up or corrections to the original case)  
597 need to be detailed on a new SAE form and faxed to the Sponsor or designated organization.

598 As a minimum, the investigator should copy Novo Nordisk when expediting SARs or SUSARs,  
599 and should report all SARs related to Novo Nordisk product to the local Novo Nordisk affiliate safety

600 department. The submission to Novo Nordisk must be within day 15 from the investigator's first  
601 knowledge about a valid case.

602

603 **14.5. Pregnancies:** Female patients must be instructed to notify the investigator immediately if they  
604 become pregnant during the trial. The investigator must report any pregnancy in patients who received  
605 Novo Nordisk provided trial product.

606

607 The investigator must follow the pregnancy until the pregnancy outcome and the newborn infant(s) until  
608 the age of 1 month. The investigator must report all information on pregnancy, including AEs in the  
609 patient, the foetus, and newborn infant. All this information must be forwarded to Novo Nordisk.

610

611 When an abnormality is reported in the foetus or newborn infant, information is needed from the male  
612 partner. Informed consent must be obtained prior to this.

613

614 **14.6 Indemnity insurance:** A written assurance indemnity or clinical trial insurance to protect the  
615 institutions from claims of non-negligent harm resulting from the clinical research and to coverage  
616 patients for untoward events will be subscribed by the principal investigator. The amount of  
617 compensations paid should be appropriate to the nature, severity, and persistence of the injury. This  
618 insurance indemnity will be in accordance with Royal decree 223/2004, of 6th February 2004, establishing  
619 the requisites regarding clinical trials.

620

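### Section 14 applies three inconsistent causality thresholds, so an event can be an adverse reaction under 14.1 and yet not be Related under 14.2

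*Combined protocol and SAP*

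**What the plan says.** Section 14.1 (Definitions) sets two causality thresholds.

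- **Adverse reaction (AR):** a causal link between "a study medication and an AE is at least a reasonable possibility, i.e., the relationship cannot be ruled" out.
- **Serious adverse reaction (SAR):** an event that is both "serious and, in the opinion of the reporting investigator, believed with reasonable probability to be due" to a study treatment. A SUSAR is "A serious adverse reaction, the nature or severity of which is not consistent with the applicable product" information, so it inherits the SAR threshold.

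Section 14.2 (Causality) sets a third. Each adverse event must be judged by a "medically qualified individual according to the following definitions", and there are only two categories.

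- **Related:** the timing fits, and "It cannot reasonably be attributed to any other cause".
- **Not Related:** "The adverse event is probably produced by the" patient's clinical state or by other therapy.

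Section 14.3 then uses relatedness. Events considered related to "the study medication as judged by a medically qualified investigator or the sponsor will be followed until" they resolve or become stable. Related events that cause withdrawal, or that are present at the end of the study, are also to be followed to a satisfactory resolution.

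Section 14.4 uses the SAR and SUSAR terms for expedited reports and for copies to the manufacturer. Initial notification does not depend on causality: "All SAEs must be reported to the Sponsor or" its delegate within one working day.

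**The concern.** The AR definition sets a low bar: it is enough that the drug cannot be excluded. The Related category sets a high one: no other attribution may be reasonable. Section 14.2 is the protocol's compulsory causality assessment, so the high bar is the one an investigator would apply when completing the form.

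Duties in 14.3 hang on the result. If an AR is not classed as Related, the specific obligation to follow it to resolution or stability is not triggered. For serious events there is a second question: whether the 14.2 assessment, or the SAR wording itself, keeps a possible reaction out of SAR and SUSAR handling.

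The situation is foreseeable in this trial. Section 5.3.9 keeps every participant on metformin, with or without a sulfonylurea, and all participants have obesity and type 2 diabetes. Other therapy and clinical state, the two alternatives named under Not Related, are therefore present in everyone. The five hospitals have no rule for settling the middle cases.

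**Working it through.** No arithmetic applies. The check is to take four kinds of event, each with plausible timing and differing only in the strength of the competing explanation, and to read each definition as written.

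| Event | AR (14.1) | SAR wording, if serious (14.1) | Related (14.2) | Not Related (14.2) |
|---|---|---|---|---|
| A. No other reasonable cause | Yes | Yes | Yes | No |
| B. Another cause is reasonable but not probable | Yes | Depends on the investigator's opinion | No, on a strict reading | No |
| C. Another cause is probable, but the drug remains a reasonable possibility | Yes | Probably not | No | Yes |
| D. Drug cause ruled out, another cause probable | No | No | No | Yes |

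**Rows A and D** agree across all definitions.

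**Row B** is the strict-reading gap. Another attribution is reasonable, so Related fails. The other cause is not probable, so Not Related fails as well. The two-category scale has no place for the event, although it is an AR.

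**Row C** is a direct contradiction. The event is an AR under 14.1 and Not Related under 14.2. This row does not depend on how Row B is read.

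**Consequence in 14.3.** For a B or C event classed as not related that does not lead to removal from treatment, the duty to follow to resolution or stability is not triggered, even if the event is still present at the end of the study. This follows from the text.

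**Consequence in 14.4, if the event is serious.** There are two routes to SAR status, and neither covers everything that the AR definition covers. If the 14.2 result is used, B and C drop out. If the SAR wording is used, inclusion requires reasonable probability, which is more than reasonable possibility. Because 14.4 does not cite 14.2, this is a risk and not a certainty.

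**The case against.** The strongest reply is that the two 14.2 categories are nearly complementary in practice. If another cause is not probable, an investigator may fairly say that the event cannot reasonably be put down to it, and so class it as Related. That is a tenable reading, and it would close Row B. It leaves Row C untouched, because a probable competing cause can coexist with a drug cause that has not been excluded.

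The reply is also right that several stronger inferences would go too far:

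- **That Related demands that no other cause be possible at all.** The text is limited to what can reasonably be attributed. The conflict with the AR definition remains, but it is smaller than that reading suggests.
- **That only related events receive any follow-up.** Section 14.3 asks for follow-up information as needed and lets the sponsor, as well as the investigator, judge relatedness. For an event that leads to removal from treatment, it requires an end-of-study assessment and supervised care until symptoms end or stabilise, with no relatedness condition. The gap is therefore confined to events that do not lead to removal.
- **That possible reactions are definitely lost from SAR and SUSAR reporting.** The SAR definition has its own test and does not refer to 14.2, and the rule on copying the manufacturer is stated as a minimum.
- **That reactions will be undercounted unevenly, or that middle cases are frequent.** The documents give no figures. The trial is double-blind, and nothing in the text suggests that misclassification would differ by arm.

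Finally, all adverse events are recorded whatever their attribution, together with any other suspect drug or device, so the information needed to reclassify is kept. Section 9 plans no analysis of related events, and the FEV1 result is not affected.

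**Conclusion.** The inconsistency is real and can be read directly from 14.1 and 14.2: three thresholds for one judgement, with at least one class of event (Row C) that is an AR and Not Related at the same time. On a strict reading, a second class (Row B) cannot be classified at all.

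The direct effect is on follow-up in 14.3, for events that do not lead to removal from treatment, including those present at study end. The effect on SAR and SUSAR handling and on copies to the manufacturer is a risk that rests on one assumption: that sites carry the 14.2 result, or the narrower SAR wording, into 14.4. Recording of adverse events and notification of serious events to the sponsor are intact.

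The number of events concerned cannot be derived from the documents. The wording conflict itself is certain; how much it would matter in practice is not.

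**What to change.** Reconcile the AR definition, the SAR definition and 14.2 so that one threshold applies throughout section 14.

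1. In 14.2, define Related with the wording that 14.1 already uses for an adverse reaction, and define Not Related as everything else, so that each event falls in exactly one category.
2. In 14.1, define a SAR as an adverse reaction that meets the seriousness criteria, so that SARs and SUSARs inherit the same threshold.
3. In 14.3 and 14.4, refer to that single definition.
4. Align the relatedness field in the eCRF.

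The cost is a few sentences and one eCRF field. The downside is that more events will be classed as related, with the follow-up and reporting work that this brings; the documents give no basis for saying how many.

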## 621 **15. PUBLICATION STRATEGY**

622

623 The diffusion of the results will follow the procedures that we are currently using. Therefore, the results  
624 will first be presented at national and international congresses and oral presentation will be prioritized.  
625 Afterwards, we will submit the papers to top journals (first quartile journals or with impact factor > 5). If a  
626 late break result is obtained this will be sent as a "Rapid Communication" to a relevant journal that allows  
627 this type of publication or it will be sent to a prestigious on-line journal (i.e. PLoS One). Simultaneously, a  
628 parallel diffusion through informative channels (newspapers, radio or TV interviews) will be conducted

629       Novo Nordisk will be informed of any intended publication related to the clinical trial results, and a  
630 period of 4 weeks will be established in order to receive Novo Nordisk comments.

631       The Novo Nordisk involvement in this clinical trial will always be acknowledged in any diffusion  
632 action related with its results.

633

